6.10 Sample Collections

The total volume of blood collected for each assessment is discussed in the laboratory manual.

7 Statistical and Analytical Plan

7.1 Primary Endpoint

- Mean change from baseline in DAS28-hsCRP score (based on 3 individual components including TJC, SJC, and hsCRP) at Week 12

7.2 Secondary Endpoints

Secondary endpoints will be evaluated at Weeks 2, 4, 8 and 12 unless otherwise stated.

- Percentage of subjects who would achieve ACR20, ACR50 and ACR70 response over time
- Change from baseline in DAS28-hsCRP score (based on 3 individual components including TJC, SJC, and hsCRP)
- Change from baseline in the tender/painful and swollen joint count (28)
- Change from baseline in the physician global assessment of disease activity by VAS
- Change from baseline in the subject global assessment of disease activity by VAS
- Change from baseline in the subject's assessment of arthritis pain by VAS
- Change from baseline in the HAQ-DI
- Change from baseline in median hsCRP values at each visit
- Safety and tolerability of SKI-O-703 compared to placebo including laboratory tests, infections, ECGs, vital signs, incidence of AEs, withdrawals due to AEs and serious adverse events (SAEs).
- PK parameters of SKI-O-592 and its metabolites (M2 and M4) from a subset of subjects per cohort on Day 1 and at Week 12, including: Cmax, Tmax, AUC0-tau, t1/2, Kel, CL/F (SKI-O-592 only), Vz/F (SKI-O-592 only), Rmet, and RAUC, as applicable
- PD parameters for the change from baseline in the percentage of activated gp53/CD63+ basophils in peripheral blood on Day 1 and at Week 12, including: Emax, TEmax, AUEC0-tau, as applicable

7.3 Exploratory Endpoint

- An assessment of PK/PD relationship between plasma concentrations of SKI-O-592, M2, and M4 and change from baseline in the percentage of activated gp53/CD63+ basophils in peripheral blood on Day 1 and at Week 12

7.4 Sample Size Calculations

Approximately 148 subjects will be enrolled in 4 cohorts (3 cohorts of SKI-O-703 and 1 cohort of placebo). Each cohort will consist of at least 37 subjects.

The study is powered to detect a difference of 0.80 in mean change from baseline to Week 12 in DAS28-hsCRP score between one of the groups treated with SKI-O-703 and the group treated with placebo. At least 37 subjects on a course of SKI-O-703 treatment are required to complete the study to show a change from baseline to Week 12 of 0.80 and higher as statistically significant with a power of 0.80 at the significance level of 0.05, using a 1-way analysis of variance and assuming a standard deviation of 1.25, compared with in the placebo group. Sample size determinations were based on the 4-component DAS28 and are likely to be similar with the 3-component DAS28 with fewer variables (Breedveld et al 2016).

Given the 1:1:1:1 ratio of SKI-O-703 100 mg BID, 200 mg BID, 400 mg BID to placebo allocation, at least 37 subjects in each treatment group are required to complete the study, therefore at least 148 subjects need to be enrolled and randomized in the study. Assuming a drop-out rate of 10%, up to 20 additional subjects may be enrolled to achieve the target number of subjects required to complete the study.

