Study Drug, Dosage, and Route of Administration	SKI-O-703 will be administered orally. Three dose levels of SKI-O-703 will be evaluated in separate cohorts: 100 mg BID, 200 mg BID, and 400 mg BID. Fourth cohort will be matching placebo.
Sample Size	At least 148 subjects will be enrolled in 4 cohorts (3 cohorts of SKI-O-703 and 1 cohort of placebo). Each cohort will consist of at least 37 subjects. The study is powered to detect a difference of 0.8 in mean change from baseline to Week 12 in DAS28-hsCRP score between one of the groups treated with SKI-O-703 and the group treated with placebo. At least 37 subjects on a course of SKI-O-703 treatment are required to complete the study to show a change from baseline to Week 12 of 0.80 and higher as statistically significant with a power of 0.80 at the significance level of 0.05, using a 1-way analysis of variance and assuming a standard deviation of 1.25, compared with in the placebo group. Sample size determinations were based on the 4-component DAS28 and are likely to be similar with the 3-component DAS28 with fewer variables. Given the 1:1:1:1 ratio of SKI-O-703 100 mg BID, 200 mg BID, 400 mg BID to placebo allocation, at least 37 subjects in each treatment group are required to complete the study, therefore at least 148 subjects need to be enrolled and randomized in the study. Assuming a drop-out rate of 10%, up to 20 additional subjects may be enrolled to achieve the target number of subjects required to complete the study.
Statistical Methods	Statistical analysis will be performed using SAS® software version 9.3 or later. The primary and secondary endpoints will be repeated for subgroups of the number of previous csDMARDs treatments (0~2 or ≥ 3), previous 1, 2 or more anti-TNF α biologic agents use (Yes or No), and specific geographic region (APAC, EMEA, and NA). The results for each efficacy endpoint will be summarized by visit and treatment for all subjects within the intention-to-treat (ITT), modified ITT (mITT), and per protocol (PP) set using descriptive statistical methods. Continuous variables will be summarized using the mean, SD, median, minimum value, and maximum value. Categorical variables will be summarized using frequency counts and percentages. Data will be listed in data listings.
Version and Date of Protocol	Version 5.0, Amendment 4; 19 Oct 2020

Table of Contents

Protocol Synopsis.....	7
Table of Contents	22
List of Tables.....	27
List of Figures.....	27
List of Abbreviations.....	28

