DAS28-CRP(4) is computed using 4 variables: swollen and tender joint count, CRP, and subject's global assessment of disease activity. DAS28-CRP(3) only includes swollen and tender joint count and CRP as subject global assessment has been excluded. DAS28-CRP(3) may seem more feasible than DAS28-CRP(4) as it does not include subject global assessment, therefore it may be less influenced by subject's mood, etc., and may be considered a more reliable measure of disease activity. Baseline and 4 months disease activity data from 239 rheumatoid arthritis patients treated with a biological agent were extracted from the Danish registry for biological treatment in rheumatology (DANBIO). DAS28-CRP(4) at baseline was 4.8 ± 1.2 versus 4.6 ± 1.1 for DAS28-CRP(3). After 4 months of biological treatment, the scores for DAS28-CRP(4) and DAS28-CRP(3) had improved by -1.39 ± 1.34 ($p < 0.0001$) and -1.18 ± 1.22 ($p < 0.0001$), respectively. It was concluded that the thresholds for low and high disease activity and for improvements were the same for the 2 scores. While DAS28-CRP(3) yielded lower scores, categorized less patients as having high disease activity level, and scores may differ in individual subjects, and was less sensitive to change than DAS28-CRP, the 2 DAS-scores were highly correlated at both baseline ($r = 0.96$, $p < 0.0001$) and at 4 months ($r = 0.97$, $p < 0.0001$). Hence, DAS28-CRP(3) and DAS28-CRP(4) agree well on group level that are relevant for analysis of group-level data in a clinical trial setting (Madsen 2011).

A sensitivity analysis will also be performed using the 4 components DAS28-hsCRP on these subjects. The clinical team will determine on a subject by subject basis how the subject's global assessment of disease activity VAS in the DAS28-hsCRP from each subject was scored, and identify subjects who consistently completed the subject's global assessment of disease activity reverse VAS scale to include in this analysis. Only subjects who completed this VAS scale in a consistent manner throughout the study will be included in this analysis; other subjects will be excluded. For subjects who will be included in this analysis using the reversed scale, the values collected will be changed using 100 minus the original value to determine the final score to be used in the analysis. The details of the subjects who will be included for this sensitivity analysis will be provided in a separate document.

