7.7 Statistical Analysis Methodology

Statistical analysis will be performed using SAS® software Version 9.3 or later. The results for each efficacy endpoint will be summarized by visit and treatment for all subjects within the ITT, mITT, and PP sets using descriptive statistical methods. Continuous variables will be summarized using the mean, SD, median, minimum value, and maximum value. Categorical variables will be summarized using frequency counts and percentages. Data will be listed in data listings.

Further details of the statistical analyses, methods, and data conventions will be described in the statistical analysis plan.

All statistical tests will be 2-sided and performed using a 5% significance level, leading to 95% CIs (2-sided). There will be no adjustments for multiplicity.

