7.7.3 Analysis of Primary Endpoint

The primary endpoint is the mean change from baseline in DAS28-hsCRP at Week 12 which is based on 3 individual components including TJC, SJC and hsCRP (see calculation in Appendix 13.6).

The mean change from baseline in DAS28-hsCRP at Week 12 between each of the active treatment groups and the placebo arm will be analyzed using an analysis of covariance (ANCOVA). The difference in mean change from baseline between each active treatment and the placebo will be estimated and the corresponding 95% CI and p-value will be calculated.

The primary endpoint will be analyzed using the ITT, mITT, and PP analysis sets. For the mITT set, results for subjects that are missing at Week 12 will be imputed using the last observation carried forward (LOCF) method.

A sensitivity analysis based on the 4-component DAS28-hsCRP (consisting of 4 individual components including TJC, SJC, hsCRP, and subject's global assessment of disease activity [VAS]; see calculation in Appendix 13.6) will be performed on the ITT set restricted to subjects who consistently completed the subject's global assessment of disease activity reverse VAS scale.

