4.3. Sample Size

Approximately 148 subjects will be enrolled in 4 cohorts (3 cohorts of SKI-O-703 and 1 cohort of placebo). Each cohort will consist of at least 37 subjects.

The study is powered to detect a difference of 0.8 in mean change from baseline to Week 12 in DAS28-hsCRP score between one of the groups treated with SKI-O-703 and the group treated with placebo. At least 37 subjects on a course of SKI-O-703 treatment are required to complete the study to show a change from baseline to Week 12 of 0.80 and higher as statistically significant with a power of 0.80 at the significance level of 0.05, using a 1-way analysis of variance and assuming a standard deviation of 1.25, compared with in the placebo group. Sample size determinations were based on the 4-component DAS28 and are likely to be similar with the 3-component DAS28 with fewer variables.

Given the 1:1:1:1 ratio of SKI-O-703 100 mg BID, 200 mg BID, 400 mg BID to placebo allocation, at least 37 subjects in each treatment group are required to complete the study, therefore at least 148 subjects need to be enrolled and randomized in the study. Assuming a drop-out of rate of 10%, up to 20 additional subjects may be enrolled to achieve the target number of subjects required to complete the study.

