7.3.2. Treatment Compliance

Treatment compliance (%) will be calculated for each subject as 100 times total dose divided by the intended total dose that should be taken over the treatment period. The intended total dose is calculated as 8 times the treatment duration. Compliance will be summarized using descriptive statistics by treatment group. The acceptable range for compliance is defined as between 80% - 120%. The number and percentage of subjects will be summarized by category $< 80\%$, $\geq 80\%$ to $\leq 120\%$, and $> 120\%$.

A subject data listing of study drug accountability will be provided, with the capsules dispensed, capsules returned, capsules taken, intended total dose and treatment compliance presented.

8. Efficacy Analysis

The primary analyses of all efficacy endpoints will be based on the ITT set, and then repeated using the PP set. The analyses of primary endpoint and secondary efficacy endpoints ACR20, ACR50 and ACR70 will also be provided based on the mITT set.

Each efficacy endpoint will be descriptively summarized by treatment group over time. In the summary for a post-baseline time point, subjects who have both values at baseline and at the time point will be included. Listings of all the efficacy endpoints will be provided by subjects.

Statistical comparisons will be performed between each of active treatment groups and the placebo group. All the statistical tests will be 2-sided and performed at a significance level of 0.05, leading to 95% CIs (2-sided). There will be no adjustment for multiplicity.

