8.2.1. Primary Analysis

The primary analysis will be conducted on observed cases, which means DAS28-hsCRP at Week 12 will be calculated only when all the three individual components (TJC28, SJC28 and hsCRP) are assessed at this visit; otherwise, DAS28-hsCRP at Week 12 will be considered as missing.

The change from baseline in DAS28-hsCRP at visit Week 12 will be analyzed using an analysis of covariance (ANCOVA) model. The model will include treatment groups as a factor and DAS28-hsCRP at baseline as a covariate. Within-group least-square (LS) means and the associated standard errors (SE), the treatment differences in LS means and the associated SEs, the 2-sided 95% CIs, the 2-sided p-values for treatment comparisons between each of active treatment group and placebo group, and the 2-sided p-values for treatment comparisons among active treatment groups (high dose vs. low dose) will be estimated and provided. Descriptive statistics of baseline, observed value and change from baseline at Week 12 will be summarized by treatment group.

The primary efficacy analyses will be performed based on the ITT set, and then repeated using the PP set.

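### Is the stated 80% power at 37 completers per arm wrong for the dose-placebo comparison?

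*Protocol*

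**What the plan says.** Protocol 7.4, the synopsis and SAP 4.3 give the same sizing statement. The target is a 0.80 difference in mean change to Week 12 between one SKI-O-703 group and placebo. "At least 37 subjects on a course of SKI-O-703 treatment are required to complete the study", and the result is to be "significant with a power of 0.80 at the significance level of 0.05, using a 1-way analysis of variance and assuming a standard deviation of 1.25". Allocation is 1:1:1:1. Up to 20 subjects beyond 148 may be enrolled to cover 10% drop-out.

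On the score used for sizing, SAP 4.3 says: "Sample size determinations were based on the 4-component DAS28 and are likely to be similar with the 3-component DAS28 with fewer variables". Protocol 7.4 has the same sentence with a citation. Protocol 6.3.1 explains that the subject global VAS was removed from the primary score because its scale had been reversed and was scored variably across sites. It reports registry data on both scores and concludes that "DAS28-CRP(3) and DAS28-CRP(4) agree well on group level".

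On the test, Protocol 7.7 says: "All statistical tests will be 2-sided and performed using a 5% significance level", with no multiplicity adjustment. The opening of SAP Section 8 says: "Statistical comparisons will be performed between each of active treatment groups and the placebo group". For the primary ANCOVA, SAP 8.2.1 says: "The model will include treatment groups as a factor and DAS28-hsCRP at baseline as a covariate".

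**The concern.** The sizing sentence describes one dose against placebo, and that contrast with the stated inputs falls short of 80% at 37 per arm. The 80% figure is the documents' only quantitative justification for the trial's size, so an overstatement would matter.

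Two further points add to the doubt. The sizing names a one-way ANOVA while the primary analysis is an ANCOVA, and no baseline-change correlation or residual SD is given. The sizing inputs also come from the 4-component score, while the primary endpoint is the 3-component score. Protocol 6.3.1 itself calls the 3-component score less sensitive to change. A reader therefore cannot look up the power of the planned test on the actual primary score.

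**Working it through.** **Inputs.** Difference 0.80, SD 1.25, n = 37 completers per arm, four arms (Protocol 7.4, SAP 4.3). Two-sided 0.05, no multiplicity adjustment (Protocol 7.7, SAP 8). Registry change: 3-component −1.18 (SD 1.22), 4-component −1.39 (SD 1.34) (Protocol 6.3.1). The baseline-change correlation r is not given and is varied below.

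**1. The plan's own figure: one-way ANOVA, four groups, one displaced by 0.80.**
- Group means (0.80, 0, 0, 0) have grand mean 0.20. The sum of squared deviations is 0.60² + 3 × 0.20² = 0.48.
- Noncentrality λ = n × 0.48 / 1.25².
- n = 36: λ = 11.06, F on (3, 140) df, power 79.4%.
- n = 37: λ = 11.37, F on (3, 144) df, power 80.6%.

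So 37 is the smallest n that reaches 80%, which matches the documents. That the sample size came from this calculation is an inference, because the documents name only the ANOVA.

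**2. The contrast the sentence describes: one dose against placebo.**
- Noncentrality δ = (0.80 / 1.25) × √(37/2) = 0.64 × 4.301 = 2.753.

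| Method at n = 37 | Power | n per arm for 80% |
|---|---|---|
| Normal approximation | 78.6% | 39 (38.3 before rounding) |
| t, four-arm pooled error, 144 df | 78.1% | 39 (80.2%) |
| t, two arms only, 72 df | 77.5% | 40 (80.7%) |

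The shortfall is 1.4 to 2.5 points, or 2 to 3 completers per arm.

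**3. Drop-out allowance.** 168 × 0.9 / 4 = 37.8 completers per arm gives 78.9% (pooled error). The extra subjects cover drop-out and add little beyond that.

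**4. The planned ANCOVA.** Residual SD = 1.25 × √(1 − r²), 143 df, assuming 1.25 is the unadjusted SD of change.

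| r (absolute value) | Residual SD | Power |
|---|---|---|
| 0 | 1.25 | 78.1% |
| 0.22 | 1.22 | 80.0% |
| 0.30 | 1.19 | 81.8% |
| 0.50 | 1.08 | 88.4% |

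The break-even correlation is about 0.22.

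**5. The 3-component score.**
- Registry SD 1.22 with the difference kept at 0.80: δ = (0.80 / 1.22) × 4.301 = 2.820, power 80.0% with no baseline adjustment.
- If the between-arm difference also shrank in the registry ratio, it would be 0.80 × 1.18 / 1.39 = 0.68. Unadjusted power would then be 72.2% with the SD scaled the same way (1.25 × 1.22 / 1.34 = 1.14), 66.2% with SD 1.22 and 64.1% with SD 1.25.

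The shrinkage is an assumption. The registry figures are changes within treated patients, not differences between randomised arms.

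**The case for a change.** The strongest case for a change is that the sentence is unsatisfactory on either reading. If 37 came from the omnibus F test, the trial was sized on a test that neither document plans to run. If it came from the pairwise contrast, 80% is about 2 points high and the claim that 37 suffice is not supported. The rescue by ANCOVA also depends on a correlation that is not stated and on 1.25 being an unadjusted SD of change, which the documents do not say. If 1.25 were already a residual SD, there would be nothing to recover.

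The 3-component point may matter more than the 2-point gap. Lower sensitivity to change could reduce the between-arm difference, and the last lines of the check show what that could cost.

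The mismatch between wording and number stands, and so does the absence of a stated power for the planned test on the primary score. What does not stand is a miscalculation or a demonstrated loss of power. Sizing without covariates and analysing with ANCOVA is common and usually conservative. The 4-component basis is disclosed openly, with a source and with registry data on both scores. The lower power figures need the registry ratio to carry over to between-arm differences, and nothing in the documents supports or excludes that.

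**Conclusion.** The stated 80% is not shown to be wrong. It reproduces at exactly 37 per arm (80.6%) with the ANOVA the documents name. The single dose-placebo contrast has about 78% power unadjusted, and a baseline-change correlation of about 0.22 closes that gap, provided 1.25 is the SD of change. With the difference held at 0.80, the Protocol's own 3-component SD of 1.22 also gives 80.0%.

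What remains is loose description and unstated planning inputs: the test behind 37, the meaning of 1.25, and a difference and SD for the 3-component score. Writing these down would not alter the sample size, the primary model, the contrasts, the significance level or any decision rule. No interim analysis or adjusted threshold depends on the power figure either. The trial's precision will come from the residual variance actually observed, and the planned confidence intervals will report it.

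Moving to the 3-component score was a fair trade-off for removing a VAS that had been scored inconsistently. Its effect on power cannot be settled from the documents, and a restated assumption would not settle it. No change to the plan follows.

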7.5 Analysis Sets

The following analysis sets will be used in the statistical analyses.

Safety set: The safety set will consist of all subjects who receive at least 1 dose of study drug (SKI-O-703 or placebo). Subjects will be analyzed according to the study treatment they receive. This population will be used for summaries of safety data.

Intention-to-Treat (ITT) set: The ITT set will consist of all subjects who receive at least 1 dose of study drug (SKI-O-703 or placebo). Subject will be analyzed according to the

treatment group to which they were randomized. This population will be used for summaries of demographic data and efficacy summaries.

Modified Intention-to-Treat (mITT) set: The mITT set will consist of all subjects who receive at least 1 dose of study drug (SKI-O-703 or placebo) and have at least 1 postbaseline assessment. This population will be used for efficacy summaries and will include imputed data for subjects who withdraw from the study prior to the Week 12 visit.

Per-protocol (PP) set: The PP set will consist of all subjects from the ITT set without important protocol deviations.

Pharmacokinetic (PK) set: The PK set will consist of all subjects who receive SKI-O-703 and have at least 1 measurable plasma concentration. Subjects who have partial data and/or major protocol deviations that may impact PK, and subjects who experience emesis, will be evaluated on a case-by-case basis and may be excluded from the PK population. This population will be used for summaries of PK data.

Pharmacodynamic (PD) set: The PD set will consist of all subjects who receive at least 1 dose of study drug (SKI-O-703 or placebo) and have at least 1 evaluable postdose PD value. Subjects who have partial data and/or major protocol deviations that may impact PD will be evaluated on a case-by-case basis and may be excluded from the PD population. This population will be used for summaries of PD data.

Pharmacokinetic (PK)/pharmacodynamic (PD) set: The PK/PD set will consist of all subjects included in both the PK and PD populations. This population will be used for the PK/PD analyses.

7.6 Description of Subgroups to be Analyzed

The primary and secondary endpoints described in Section 7.1 and Section 7.2 will be repeated for the following subgroups:

- The number of previous csDMARDs treatments (0~2 or ≥ 3)
- Previous 1, 2 or more anti-TNF α biologic agents use (Yes or No)
- Specific geographic region (APAC, EMEA, and NA)

7.7 Statistical Analysis Methodology

Statistical analysis will be performed using SAS® software Version 9.3 or later. The results for each efficacy endpoint will be summarized by visit and treatment for all subjects within the ITT, mITT, and PP sets using descriptive statistical methods. Continuous variables will be summarized using the mean, SD, median, minimum value, and maximum value. Categorical variables will be summarized using frequency counts and percentages. Data will be listed in data listings.

Further details of the statistical analyses, methods, and data conventions will be described in the statistical analysis plan.

All statistical tests will be 2-sided and performed using a 5% significance level, leading to 95% CIs (2-sided). There will be no adjustments for multiplicity.

